**REVISION HISTORY**

| Revision # | Version Date | Summary of Changes   | Consent Change? |
|-------------------|---------------------|---|------------------------|
| 1                 | May 15 2022         | Change in number of treatments/duration of study   | Yes                    |
| 2                 | September 13 2022   | Addition of HairMetrix to secondary endpoint and study design   | Yes                    |
| 3                 | January 4, 2023     | Edit to HairMetrix to only occur before treatment and edited the frequency of control swabs to room air   | Yes                    |
| 4                 | March 2, 2023       | -Changed age of enrollment eligibility to 18-50 years old
- Administrative updates
-On page 11-updated sentence to indicate the treatment is over a two-week period.
-Updated the section 5.3 page 12 that participation will last approximately 2.5 weeks
-Removed the words "before treatment" on page 13 | Yes                    |
| 5                 | August 5, 2023      | -Changed total enrollment to "n=20-25", pg 10
- Updated total enrollment to state "A total of up to 25 subjects" on pg 10
-Deleted 20 males and 20 females on pg 10   | No                     |
|                   |                     |   |                        |
|                   |                     |   |                        |

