## 5.0 Procedures Involved

5.1 Study Design: This is a research study utilizing scalp swabs to evaluate the efficacy of the Venus Glow™ device treatment on the scalp microbiome. Healthy participants who have not been diagnosed with scalp or hair disease will be followed over a period of 2 weeks to assess their scalp microbiome and see how well the investigational device works on decreasing the microbe burden of the scalp.

*Total Enrollment (N= 20-25):* A total of up to 25 subjects between the ages of 18-50 years with different self-reported ethnicities and evaluated skin and hair types will be enrolled in the study.

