7.2.3 Future analysis of genotypes: N/A

## 8.0 Study Population

8.1 Inclusion Criteria:

Participants must meet all of the inclusion criteria.

- All individuals between 18-35 years of age
- Ability to understand study procedures and to comply with them

8.2 Exclusion Criteria:

All candidates meeting any of the exclusion criteria at baseline will be excluded from participation in this study.

- Non-English speakers
- Exclusion related to pregnancy, lactation, or has plans to become pregnant over the course of the study
  - Based on self-report from the participant
- Current scalp or hair disease diagnosis
- Using oral or topical antimicrobial medication 4 weeks prior to their baseline visit or in the duration of the study

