**10.0 Local Number of Participants**

## MEDICAL PROTOCOL (HRP-590)

PROTOCOL TITLE: Effect of mechanical intervention on the scalp microbiome: setting the stage for the future management of cicatricial alopecias

VERSION DATE: 05 August 2023

*10.1 Local Number of Participants to be Consented:* 40 participants are needed for data analysis and we anticipate needing to consent 55 people to reach that goal.

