## **15.0 Statistical Considerations**

*15.1 Data Analysis Plan:*

The primary analysis will evaluate whether there is a difference in the baseline and 2-week change in the relative abundance of pre-specified bacteria (approx. 20) between the device-treated portion of the scalp and the non-treated portion. In order to account for the within-subject correlation, mixed-effects models will be performed. As a secondary analysis, we will compare the HairMetrix images and analyze how various demographic and clinical factors such as sex and skin type impact the effect of the device.

*15.2 Power Analysis:*

Limited data are available to inform a power/sample size estimate. However, if there is a total of 38 subjects (40 initial, with 5% dropout), then we will have pre- and post-treatment data for 38 device-treated, and 38 non-treated portions of the scalp. Even when ignoring the within-subject correlation, this will allow us to have 80% power to detect an effect size of 0.7 (difference in the baseline to week 1 change between groups), assuming an alpha of 0.05.

*15.3 Data Integrity:*

- The study monitor will ensure that the investigation is conducted according to protocol design and regulatory requirements. The monitor will provide ongoing monitoring of data validity and regulatory issues (e.g., eligibility determinations, consent form process, serious adverse event reporting, IRB actions, disclosures of conflict of interest).
- Study records will be monitored at regular intervals by the study monitor. The monitor will perform source data verification and as such must be given access to the subject's primary source documentation, such as paper or electronic medical records such as consent to participate in the study, visit dates, demographic information, adverse events, concomitant medications, drug accountability, etc. that support data entries in the CRF.

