22.2 International Research: N/A

## 23.0 Multi-Site Research: N/A

## 24.0 Coordinating Center Research

24.1 Role: N/A

24.2 Responsibilities: N/A

24.3 Oversight: N/A

24.4 Collection and Management of Data: N/A

## 25.0 Resources Available

25.1 Resources Available:

- The dermatology research interns/fellows will be participating in study procedures with the support of the PI. No students will be involved in this study.
- The number of recruitable participants is appropriate for the time period of three years. Forty participants are needed for data analysis and we anticipate needing to consent 55 people to reach that goal.
- One to two hours of PI/study staff time will be dedicated to each visit.
- Facilities for this study include the M Health Fairview Maple Grove Clinic, M Health Fairview Clinics and Surgery Center, and the clinical research room in the University of Minnesota Department of Dermatology.
- There are no anticipated severe consequences of the treatment, however, two of the sites are in the clinical setting and one is connected to the UMMC Hospital.
- The PI or Co-PI will be present for all treatments, in addition to dedicated dermatology research staff.

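### The power statement in 15.2 assumes 40 enrolled and 38 analysed, but 5.1 now caps enrolment at 25; on 15.2's own unpaired basis, power at 0.7 falls to about 56–66% per taxon (two-sided, 5% dropout)

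*Combined protocol and SAP*

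**What the plan says.** Four places in the current version (5 August 2023) of the combined protocol and SAP give sample-size figures.

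- **5.1 Study Design** sets total enrolment at 20–25: "A total of up to 25 subjects between the ages of 18-50 years".
- **15.2 Power Analysis** rests on the condition "if there is a total of 38 subjects (40 initial, with 5% dropout"), giving 38 treated and 38 untreated scalp portions. It concludes: "Even when ignoring the within-subject correlation, this will allow us to have 80% power to detect an effect size of 0.7", at an alpha of 0.05.
- **10.1 Local Number of Participants** states: "40 participants are needed for data analysis and we anticipate needing to consent 55 people to reach that goal".
- **25.1 Resources Available** repeats it: "Forty participants are needed for data analysis and we anticipate needing to consent 55 people".

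Section 15.1 makes the primary outcome the "relative abundance of pre-specified bacteria (approx. 20") and plans mixed-effects models to handle the within-subject correlation. Section 12.2 leaves withdrawn participants out of the analysis.

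**The concern.** A trial capped at 25 cannot yield 38 or 40 analysed participants. The protocol's only power statement therefore describes a sample that it no longer plans to enrol, and no other section restates it. The figures also disagree among themselves: 10.1 and 25.1 need 40 for analysis, whereas 15.2 analyses 38 of 40 enrolled.

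The 80% in 15.2 is offered as a floor that holds without any credit for pairing. If that floor has gone, a reader cannot tell what the trial can detect without a correlation that the documents do not give. Meanwhile 10.1 and 25.1 give staff and the IRB targets that 5.1 does not allow.

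The revision history is consistent with an edit that was not carried through, since revision 5 lists enrolment changes on page 10 only. The conflict does not depend on the log; the current sections show it on their own.

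**Working it through.** **Inputs from the documents.** Enrolment 20–25 (5.1). Dropout 5%, effect size 0.7, alpha 0.05, sides treated as independent (15.2).

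**Assumptions, because 15.2 is silent.** Two-sample t-test, two-sided, 0.7 read as a standardised difference, one taxon, no multiplicity adjustment.

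**1. Analysed numbers**

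- Planned in 15.2: 40 × 0.95 = 38.
- Now: 20 × 0.95 = 19 and 25 × 0.95 = 23.75, so 19 to 23–24.

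**2. The plan's own figure**

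Power is taken from the noncentral t distribution with 2n − 2 degrees of freedom and noncentrality d√(n/2). At n = 38 per side and d = 0.7, the noncentrality is 0.7 × √19 = 3.05 and power is 85.3%. The effect detectable with 80% power at n = 38 is 0.651. So 15.2 does not reproduce exactly, but it fits a detectable effect of 0.65 rounded up to 0.7. The assumed method is a fair reading of it.

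**3. The same method at the current sample**

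| Analysed per side | Power at 0.7, two-sided | Power at 0.7, one-sided | Effect detectable at 80%, two-sided |
|---|---|---|---|
| 38 (15.2) | 85.3% | 91.6% | 0.65 |
| 25 (no dropout) | 67.9% | 78.7% | 0.81 |
| 24 | 66.1% | 77.2% | 0.83 |
| 23 | 64.1% | 75.6% | 0.84 |
| 19 | 55.6% | 68.2% | 0.93 |

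Even the most favourable row, all 25 analysed and a one-sided test, stays below 80%.

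**4. What the pairing could restore**

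Let rho be the correlation between the changes on the two sides. The paired effect is dz = 0.7 / √(2(1 − rho)), tested with a paired t-test, two-sided 0.05.

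| Analysed | rho = 0 | rho = 0.25 | rho = 0.5 | rho needed for 80% |
|---|---|---|---|---|
| 24 | 64.2% | 76.5% | 90.7% | 0.31 |
| 23 | 62.2% | 74.5% | 89.4% | 0.34 |
| 19 | 53.3% | 65.4% | 82.3% | 0.47 |

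At 38 analysed, paired power is 84.4% even at rho = 0. The old sample needed no assumption about correlation; the current one does.

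**The case against.** The strongest reply is that 15.2 offers the unpaired figure as a conservative one, opens by admitting that few data exist, and is phrased conditionally. The analysis in 15.1 is a mixed model that uses the pairing, so actual power at 0.7 may still reach 80%. That is correct, and it limits the finding: no loss of power in the primary analysis has been shown. What has been shown is that the stated floor no longer holds and that nothing replaces it.

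Three narrower points also carry weight.

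- The 56–66% range needs its conditions beside it: two-sided testing and 5% dropout carried over. One-sided, it is 68–77%. The two-sided reading suits 15.1, which asks whether there is a difference, although 3.1 hypothesises a decrease.
- Setting the stated 80% against 56–66% is not like for like. By one method throughout, the fall is from 85%.
- The enrolment that would keep an unpaired 80% at 0.7 depends on sidedness. Two-sided it needs 34 analysed (34 / 0.95 = 35.8, so 36 enrolled, 11 above the cap). One-sided it needs 26 analysed (26 / 0.95 = 27.4, so 28 enrolled, 3 above the cap).

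A restated single-taxon figure will also not describe the whole primary analysis, which covers about 20 taxa. Nor does it settle whether the powered change is the 2-week one in 15.1 or the week 1 one in 15.2. These limit what a corrected 15.2 can claim; they do not remove the conflict.

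**Conclusion.** The concern holds and must be fixed. Section 5.1 contradicts 15.2, 10.1 and 25.1 in current text, and no section reconciles them. On 15.2's unpaired basis, with a two-sided t-test, 5% dropout and one unadjusted taxon, power at 0.7 is about 56% with 19 analysed and 66% with 24. No choice of sidedness within the cap of 25 brings the unpaired figure to 80%.

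Whether the mixed model reaches 80% at 0.7 turns on a left–right correlation of changes of about 0.31 (24 analysed) to 0.47 (19 analysed), for which the documents give no value. The sample-size contradiction is certain; the size of the power loss rests on the assumptions listed.

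**What to change.** Rewrite 15.2 for 20–25 enrolled and 19 to 23–24 analysed, per single taxon, naming the test, the sidedness and the change being compared. Either form will do:

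- **Unpaired.** About 56–66% power at 0.7, or 80% power for an effect of about 0.83–0.93 (two-sided).
- **Paired.** Power over an explicit range of correlations, as in the second table of the working, with the range labelled as an assumption.

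Then bring the numbers for analysis and consent in 10.1 and 25.1 into line with 5.1 and the revised 15.2, and settle 40 against 38.

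The cost is wording only, with no extra participants. The unpaired form gives a less favourable figure; the paired form depends on a correlation that the sponsor would have to justify.

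Separately, and with no bearing on power, the age range needs reconciling: 5.1 enrols ages 18–50, while 8.1 still reads "All individuals between 18-35 years of age".

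### The power statement in 15.2 is on the safe side at 38 subjects but does not carry over to the 20 to 25 now planned; it needs a paired calculation with a named SD and correlation range

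*Combined protocol and SAP*

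**What the plan says.** The power statement is one sentence in 15.2, introduced by a remark that little data exist to inform it. It starts from "38 subjects (40 initial, with 5% dropout", which gives "pre- and post-treatment data for 38 device-treated, and 38 non-treated portions of the scalp". It then says: "Even when ignoring the within-subject correlation", this provides "80% power to detect an effect size of 0.7", where the effect is the "difference in the baseline to week 1 change between groups", "assuming an alpha of 0.05". It names no test, sidedness, standard deviation or correlation.

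Section 15.1 plans a different kind of analysis, one that uses the pairing: "In order to account for the within-subject correlation, mixed-effects models will be performed".

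Section 5.1 now sets enrolment at 20 to 25. The revision history dates that change to August 2023. Section 15.2 was not updated with it, and 10.1 and 25.1 still give 40 for analysis.

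**The concern.** This sentence is the plan's only justification of its sample size, and three things about it invite a check.

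- The printed power does not come out of the printed inputs if 0.7 is taken as exact.
- The calculation is for independent groups, while the design compares two sides of the same head.
- It rests on a sample size that 5.1 no longer has.

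The practical question is whether a reader of the current protocol can still rely on 80% power at 0.7. If only the 38 were replaced in the existing calculation, the result would still be an unpaired figure for an effect whose SD is not identified.

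**Working it through.** **Inputs from the documents.** 38 portions per side, effect 0.7, alpha 0.05 and dropout 5% (15.2); enrolment 20 to 25 (5.1). Applying the plan's dropout, 20 × 0.95 = 19 and 25 × 0.95 = 23.75, so about 19 to 24 analysed.

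**Assumptions.** Two-sided test. One outcome at alpha 0.05, as 15.2 has it. rho is the correlation between the two sides' changes. A paired t-test on the between-side difference in change stands in for the mixed model.

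**Step 1. The plan's own figure, unpaired, n = 38.** Noncentral t with 2n − 2 degrees of freedom and noncentrality d × sqrt(n/2) = 0.7 × sqrt(19) = 3.05.

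- Power is 85.3% (normal approximation 86.2%, one-sided t 91.6%). None of these is 80%.
- Solving instead for the effect at 80% power gives 0.651 by the t-test, which prints as 0.7 at one decimal. The normal approximation gives 0.643, which would print as 0.6.
- An effect of exactly 0.7 needs about 33 per side (79.97%; 34 gives 81.2%).

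**Step 2. The analysis in 15.1, paired, n = 38.** If 0.7 is in units of the SD of one side's change, SD(difference) = SD(change) × sqrt(2(1 − rho)). The standardised paired effect is then dz = 0.7 / sqrt(2(1 − rho)), with noncentrality dz × sqrt(n) and n − 1 degrees of freedom.

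| rho (assumed) | Power, n = 38 |
|---|---|
| −0.3 | 74.1% |
| 0 | 84.4% |
| 0.3 | 94.4% |
| 0.5 | 98.7% |

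The dz detectable with 80% power at n = 38 is 0.467. Power is therefore at least 80% at 0.7 when rho ≥ 1 − (0.7/0.467)²/2, or about −0.12.

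**Step 3. The enrolment now in 5.1.** The same formulas at effect 0.7:

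| Basis | n = 19 | n = 24 |
|---|---|---|
| Unpaired, as in 15.2 | 55.6% | 66.1% |
| Paired, rho = 0 | 53.3% | 64.2% |
| Paired, rho = 0.25 | 65.4% | 76.5% |
| Paired, rho = 0.5 | 82.3% | 90.7% |

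The dz detectable with 80% power is 0.680 at n = 19 and 0.597 at n = 24. The rho needed for 80% power at 0.7 is therefore:

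- n = 19: 1 − (0.7/0.680)²/2 = 0.47
- n = 24: 1 − (0.7/0.597)²/2 = 0.31

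The detectable effect, dz × sqrt(2(1 − rho)), is 0.96 (n = 19) to 0.85 (n = 24) at rho = 0, 0.83 to 0.73 at 0.25, and 0.68 to 0.60 at 0.5.

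**Step 4. The unnamed SD.** If 0.7 is instead in units of the SD of the between-side difference, dz = 0.7 directly, and power is 82.3% (n = 19) or 90.7% (n = 24) whatever rho is. So at n = 19 the same printed 0.7 means 82% on one scaling and 53% on the other at rho = 0. At n = 38 the choice hardly matters: 98.7% against 84.4%, both above 80%.

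**The case against.** The strongest defence is that nothing is materially wrong at 38 subjects, and that is correct.

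- The gap between 80% and 85.3% is what one would see if 0.651 had been rounded to one decimal. This is likely, though not proven.
- The literal discrepancy understates power, so it promises nothing the design would not deliver.
- The unpaired basis is disclosed, and the wording offers it as a lower bound. Step 2 shows that the lower bound holds at zero and even slightly negative correlation. A clearly negative correlation between two sides of one scalp would be needed to break it, and nothing in the documents suggests one.

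A reader might therefore infer too much in two ways. One is that 15.2 contains a consequential arithmetic error. The other is that it used the wrong test and left the 38-subject design short of power. The documents support neither.

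It can also be said that the low figures in step 3 come from the smaller enrolment and not from the pairing. That is largely true, and it is why this belongs with the correction of the outdated sample size. But changing the number alone would not settle the matter. At 19 to 24 the answer depends on the scaling of 0.7 and on rho, as it did not at 38, and 15.2 gives neither.

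**Conclusion.** Wrong as written for the current design, at low severity. For 38 subjects the statement is imprecise and conservative. For 19 to 24 analysed it does not hold on its own unpaired basis, where power at 0.7 is about 56% to 66% and not 80%. On a paired basis, scaled by the SD of one side's change, it holds only if rho is at least about 0.47 (n = 19) or 0.31 (n = 24).

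A further inference would be that the current trial is underpowered. The documents do not establish that either: at rho = 0.5, or if 0.7 is scaled by the SD of the between-side difference, power exceeds 80%. What can be said is that 15.2 no longer shows what the power is.

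The conclusion assumes a two-sided test, the plan's 5% dropout, complete pairs and a single outcome at 0.05. Two other mismatches within section 15 are separate and not counted here: 15.1 analyses the "relative abundance of pre-specified bacteria (approx. 20" with no stated adjustment, and it refers to a 2-week change where 15.2 uses week 1.

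**What to change.** Replace the power sentence in 15.2 with a paired calculation that matches 15.1, for the number actually to be analysed. It should state:

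- whether the effect is scaled by the SD of one side's change or by the SD of the between-side difference;
- the sidedness of the test;
- a range for rho, marked as assumed if no data support it;
- the resulting power or detectable effect across that range. The tables and detectable effects in the working can serve as a template.

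If the unpaired figure for 38 is kept for reference, print it as 85% power at 0.7 or 80% power at 0.65. Make the change together with the correction of the sample size in 10.1, 15.2 and 25.1.

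The cost is one rewritten paragraph, with no added participants or procedures. The downside is that the stated power becomes less favourable unless a clearly positive rho can be justified.

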## MEDICAL PROTOCOL (HRP-590)

PROTOCOL TITLE: Effect of mechanical intervention on the scalp microbiome: setting the stage for the future management of cicatricial alopecias

VERSION DATE: 05 August 2023

- The PI will be provided copies of monitoring reports shortly after the monitoring visit. Findings will be noted and followed up in the subsequent monitoring visit.

### 16.0 Health Information and Privacy Compliance

16.1 Select which of the following is applicable to your research:

My research does not require access to individual health information and therefore assert HIPAA does not apply.

I am requesting that all research participants sign a HIPCO approved HIPAA Disclosure Authorization to participate in the research (either the standalone form or the combined consent and HIPAA Authorization).

I am requesting the IRB to approve a Waiver or an alteration of research participant authorization to participate in the research.

An external IRB (e.g. Advarra) is reviewing and we are requesting use of the authorization language embedded in the template consent form in lieu of the U of M stand-alone HIPAA Authorization. Note: External IRB must be serving as the privacy board for this option.

16.2 Identify the source of Private Health Information you will be using for your research (Check all that apply)

I will use the Informatics Consulting Services (ICS) available through CTSI (also referred to as the University's Information Exchange (IE) or data shelter) to pull records for me

I will collect information directly from research participants.

I will use University services to access and retrieve records from the Bone Marrow Transplant (BMPT) database, also known as the HSCT (Hematopoietic Stem Cell Transplant) database.

I will pull records directly from EPIC.

I will retrieve record directly from axiUm / MiPACS

I will receive data from the Center for Medicare/Medicaid Services

I will receive a limited data set from another institution

Other.

16.3 Explain how you will ensure that only records of patients who have agreed to have their information used for research will be reviewed.

Patients who have opted out of research in their medical record only be approached by clinical staff to assess interest in participation in the study.

## MEDICAL PROTOCOL (HRP-590)

PROTOCOL TITLE: Effect of mechanical intervention on the scalp microbiome: setting the stage for the future management of cicatricial alopecias

VERSION DATE: 05 August 2023

16.4 Approximate number of records required for review: N/A

16.5 Please describe how you will communicate with research participants during the course of this research. Check all applicable boxes

This research involves record review only. There will be no communication with research participants.

Communication with research participants will take place in the course of treatment, through MyChart, or other similar forms of communication used with patients receiving treatment.

Communication with research participants will take place outside of treatment settings. If this box is selected, please describe the type of communication and how it will be received by participants.

Participants may self-refer if they become aware of the study through these recruitment materials or word of mouth referrals. Individuals who respond to the recruitment materials will be taken through a phone screening questionnaire.

16.6 Explain how the research team has legitimate access to patients/potential participants:

If a potential participant is identified at the Department of Dermatology at the University of Minnesota Clinics and Surgery Center or Maple Grove Clinic, the attending provider will briefly introduce the study and ask if a member of the study team may come in to talk with them. If the potential participant agrees, the investigator and/or study coordinator will describe the study in detail, answer any questions the potential participant may have and describe next steps. All investigators and study staff will be trained in privacy and confidentiality requirements for conducting research at Fairview facilities.

16.7 Location(s) of storage, sharing and analysis of research data, including any links to research data (check all that apply).

In the data shelter of the [Information Exchange \(IE\)](#)

Store       Analyze       Share

In the Bone Marrow Transplant (BMT) database, also known as the HSCT (Hematopoietic Stem Cell Transplant) Database

Store       Analyze       Share

In REDCap ([recap.ahc.umn.edu](http://recap.ahc.umn.edu))

Store       Analyze       Share

In Qualtrics ([qualtrics.umn.edu](http://qualtrics.umn.edu))

Store       Analyze       Share

